**Setting and participants**

Participants joined the digital OA self-management and education program (see Intervention below for details), through recommendation by their local orthopaedic surgeon or physiotherapist, and via online advertisements and campaigns placed on search engines and social networks. Included participants had a radiographic and or clinical diagnosis of hip or knee OA from a physical therapist or physician (95% of all patients at the date of data extraction). Individuals without a prior diagnosis had clinical OA confirmed by an orthopaedic surgeon or physiotherapist via telephone (diagnosis according to NICE UK criteria and Swedish National Guidelines, and confirming the absence of any red flag symptoms), or if deemed necessary were recommended to seek face-to-face care before inclusion in the program.

All data for the present study were extracted from the digital self-management program data registry on the 22nd of March 2021. Criteria for inclusion in the primary data extraction were:

- Having registered in the program and had the first telephone contact with the physiotherapist assigned to the patient, and enrolled between March 1, 2018 and November 30, 2020.
- Having reported hip or knee as most symptomatic (index) joint
- Having provided 3-month follow-up data on or before February 28, 2021

These selection criteria resulted in 14006 eligible participants.

Adherence was defined as the percentage of completed activities (exercises, and text or video lessons on OA, with quizzes on lesson material) per the pre-defined period of 12 weeks. A cut-off of 80% or higher adherence corresponds to the National Recommendations for first-line knee and hip OA treatment by the Swedish National Board of Health and Welfare (1).

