In all studies we will conduct subgroup analyses by index joint (knee & hip) if data allows. Moreover, since the rate of dropout between the baseline and 3 months follow up might be different across age groups, we will apply inverse probability weighting to account for this.

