**Table 1**

	Reported only at follow-up	Reported at both baseline and follow-up	JA-ages-usage-outcomes	
	QUESTIONS	Total number of participants	Baseline	3 months
Demographics	work_situation	14006	14006	0
	educational_level	14006	14006	0
Comorbidities	other_health_problems.diabetes	14006	14006	0
	other_health_problems.lung_disease	14006	14006	0
Health	other_health_problems.balance_troubles	14006	14006	0
	other_health_problems.rheumatoid_arthritis	14006	14006	0
	other_health_problems.cardiovascular_disease	14006	14006	0
	other_health_problems.causing_walking_difficulties	14006	14006	0
	overall_health	14006	14006	14006
	specific_joint	14006	14006	14006
	specific_joint_pain	14006	14006	14006
	pain_in_other_joints	14006	14006	0
	pain_improved	0	0	4329
	pain_locations	0	0	
	exercise_choice	14006	14006	14006
	physical_activity_choice	14006	14006	14006
	difficulty_walking	14006	14006	14006
	afraid_to_get_hurt_by_movement	14006	14006	14006
	patient_acceptable_symptom_state	14006	14006	14006
	motivation_readiness	14006	14006	0
	overall_health_improved	0	0	4329
	physical_function_improved	0	0	4329
	considers_treatment_failed	0	0	8857
	wants_operation	14006	14006	14006
	invasive_operation_scheduled	2337	2337	2176
	arthroscopy_performed_on_specific_joint	14006	14006	0
	invasive_operation_type_scheduled	299	299	0
	invasive_operation_cancelled	0	0	1571
Medication	invasive_medicines_selections			
	invasive_medicines_changed			
EQ-5D	eq5d.mobility	14006	14006	14006
	eq5d.self_care	14006	14006	14006

	eq5d.pain_discomfort	14006	14006
	eq5d.usual_activities	14006	14006
	eq5d.anxiety_depression	14006	14006
HOOS-PS	hoos.running_difficulty		
	hoos.sitting_difficulty		
	hoos.descending_stairs_difficulty		
	hoos.getting_out_of_bath_difficulty		
	hoos.pivoting_loaded_leg_difficulty		
KOOS-PS	koos.squatting_difficulty		
	koos.sitting_up_difficulty		
	koos.bending_over_difficulty		
	koos.twisting_knee_difficulty		
	koos.laying_on_knee_difficulty		
	koos.putting_on_socks_difficulty		
	koos.rising_out_of_bed_difficulty		
Work productivity	wpai.employed		
	wpai.hours_actually_worked		
	wpai.oa_productivity_effect		
	wpai.oa_regular_activities_effect		
	wpai.missed_working_hours_due_to_oa		
	wpai.missed_working_hours_due_to_other_reasons		
JA	ja_like		
	recommend_others		
	therapist_appreciation		
Other	free_text_medical_information		
HIP new	hip_satisfaction_now	0	3956
	hip_satisfaction_quality	0	3956

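### Only participants with 3-month data are extracted, so the planned inverse probability weighting for dropout has no dropouts to model and cannot correct the age comparisons

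*Protocol*

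**What the plan says.** In Statistical analysis, the closing paragraph on subgroups and dropout names a threat and a remedy: "the rate of dropout between the baseline and 3 months follow up might be different across age groups, we will apply inverse probability weighting". It does not say in which population the weights are to be estimated.

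Setting and participants describes one source: "All data for the present study were extracted from the digital self-management program data registry", on a single date, 22 March 2021. Under the words "Criteria for inclusion in the primary data extraction were" it lists three conditions:

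- a first physiotherapist call, and being "enrolled between March 1, 2018 and November 30, 2020"
- hip or knee as index joint
- "Having provided 3-month follow-up data on or before February 28, 2021"

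It concludes: "These selection criteria resulted in 14006 eligible participants".

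Table 1 gives total, baseline and 3-month counts for each item. The row for the first main endpoint reads "specific_joint_pain 14006 14006 14006".

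**The concern.** Inverse probability weighting for loss to follow-up asks, for each person observed at 3 months, how likely someone with that baseline profile was to be observed. Answering that needs the baseline records of people who were not observed. The third extraction criterion removes exactly those people, so the population and the correction do not fit together.

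The protocol itself identifies age-related dropout as a threat and states no other safeguard against it. If the weighting does nothing, the age contrasts in pain and chair rise are completer-only comparisons that a reader would take to be adjusted for dropout. The Oaxaca-Blinder step then decomposes a gap that partly reflects who stayed, and may attribute that part to covariates whose means differ only because of selection.

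The adherence comparison uses the same people. It is plausible, though the protocol does not say so, that those without 3-month data are mostly low adherers. If the uptake question also used this extract, it would undercount registrations.

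**Working it through.** **1. Dropout in the defined data set.** Inputs: 14006 eligible (Setting and participants); 14006 baseline and 14006 follow-up pain scores (Table 1).

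- Retention = 14006 / 14006 = 1.000.
- Dropouts = 14006 − 14006 = 0.

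The table agrees with the entry rule: there is no loss because loss was excluded.

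**2. What the weights become.** The weight is w = 1 / P(observed at 3 months | age group, baseline covariates). With an indicator of 1 for all 14006, a logistic response model has no variation to fit and its fitted probabilities go to 1. Every w equals 1, so the weighted and unweighted age contrasts in pain are identical.

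**3. Possible size of the uncorrected bias.** The protocol gives no dropout rate, standard deviation or age-group sizes. All of these are assumed:

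- response c1 = 0.60, 0.70 or 0.75 in those aged 59 or under
- response c3 = 0.80 in those aged 70 or over
- non-responders improve d = 0.5, 1.0 or 1.5 NRS points less, equally in both groups
- standard deviation of change 2.2
- group shares of about 25% and 33% of 14006, that is 3502 and 4622

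Among completers, a group's mean improvement is overstated by (1 − c)·d. The error in the age contrast is therefore (1 − c1)·d − (1 − c3)·d.

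- Smallest: 0.25 × 0.5 − 0.20 × 0.5 = 0.125 − 0.100 = 0.025.
- Largest: 0.40 × 1.5 − 0.20 × 1.5 = 0.60 − 0.30 = 0.30.
- Standard error of the contrast: 2.2 × √(1/3502 + 1/4622) = 0.049.
- Ratio: 0.025 / 0.049 ≈ 0.5 up to 0.30 / 0.049 ≈ 6.

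**4. Whether the method would work on the right population.** An illustrative simulation used 600,000 people in three equal-probability age groups with no true age difference. One baseline covariate shifted the outcome by 0.6 points per SD and shifted completion with logit slopes of 0.9, 0.6 and 0.3 from youngest to oldest. The weights used the known completion probabilities. The table shows unadjusted mean differences from the youngest group (middle; oldest).

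| Dropout at the covariate mean, youngest to oldest | All registrants | Completers, weight 1 | Completers, weighted to all registrants |
|---|---|---|---|
| 40 / 30 / 25% | −0.008; −0.001 | −0.099; −0.157 | −0.013; −0.010 |
| 60 / 40 / 30% | 0.015; 0.009 | −0.131; −0.223 | 0.007; −0.001 |

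Completer-only analysis creates an age gap where there is none. Weighting to the full set of registrants removes it. This is a favourable case for weighting, because selection depends only on a measured covariate and the weights are known exactly.

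**The case against.** **A compatible reading exists.** The three criteria are attached to a primary extraction, and the sentence about all data fixes only the registry and the date. The 14006 could be the outcome set, with weights estimated on everyone enrolled, as is usual. Details of the weight model can be left to an analysis plan, and the flowchart, which is not shown, may account for non-responders. However, no wider extraction is described anywhere. Flowchart counts would not supply the individual covariates a weight model needs. An analysis plan could repair this only by overriding the stated criterion or adding records the protocol does not mention.

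**Not every outcome is complete within the 14006.** HOOS-12 has 3541 baseline and 3956 follow-up answers, KOOS-12 has 5026 and 5721, and Table 1 has no row for chair rise. This stands in part: constant weights are demonstrated for pain and the other fully reported items, not for chair rise. But weighting for missing items among people who returned 3-month data addresses a different problem and does not undo selection on having returned them.

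**The magnitude is assumed and modest.** This also stands. The worst assumed value, 0.30, is under a third of the protocol's 1-point threshold, and standard errors are small at this sample size for any bias. The formula counts the whole responder gap, whereas weighting removes only what measured covariates explain. The planned regressions already adjust for the baseline value and then for other covariates, which would absorb some of it.

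**Availability of records.** The protocol does not state that baseline records of non-responders can be retrieved, so the low cost of the fix is likely but unverified.

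**Conclusion.** The point holds on the protocol as written. For pain, the dropout to be weighted for is zero by construction and the weighting changes nothing. For chair rise, item completeness cannot be judged from Table 1, but people without 3-month data are excluded all the same, so the correction named in the plan is equally unavailable. This conclusion needs no assumed figures.

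The size does. Under the stated assumptions the pain contrast is off by 0.025 to 0.30 NRS points. That would not by itself amount to a clinically important difference by the protocol's own threshold. It could produce an apparently well-established age difference at a sample size the protocol calls more than sufficient, and that difference would then be decomposed as if it were real. Because the protocol claims a correction it cannot make, this should be settled before analysis.

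**What to change.** Drop the 3-month-data criterion from the extraction. Extract everyone who meets the first two criteria: first call completed and enrolled from 1 March 2018 to 30 November 2020, with hip or knee as index joint. The 14006 then become the responders within that set. Fit the response model in the full set on age group, baseline pain, the other baseline covariates and enrolment date. Enrolment date belongs there because the last enrollees had only 90 days to the follow-up cut-off, against 84 days for 12 weeks. Apply the weights to the responders in the pain and chair-rise regressions and in the decompositions. Report numbers enrolled and responding by age group. Any weighting for incomplete items should be described separately.

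The cost is one wider query of the same registry, revised wording in Setting and participants and in Statistical analysis, and slightly wider confidence intervals. If the non-responders' baseline records cannot be obtained, remove the weighting statement and label the age comparisons as completer-only.

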**Table 1**

	Reported only at follow-up	Reported at both baseline and follow-up	JA-ages-usage-outcomes	
	QUESTIONS	Total number of participants	Baseline	3 months
Demographics	work_situation	14006	14006	0
	educational_level	14006	14006	0
Comorbidities	other_health_problems.diabetes	14006	14006	0
	other_health_problems.lung_disease	14006	14006	0
Health	other_health_problems.balance_troubles	14006	14006	0
	other_health_problems.rheumatoid_arthritis	14006	14006	0
	other_health_problems.cardiovascular_disease	14006	14006	0
	other_health_problems.causing_walking_difficulties	14006	14006	0
	overall_health	14006	14006	14006
	specific_joint	14006	14006	14006
	specific_joint_pain	14006	14006	14006
	pain_in_other_joints	14006	14006	0
	pain_improved	0	0	4329
	pain_locations	0	0	
	exercise_choice	14006	14006	14006
	physical_activity_choice	14006	14006	14006
	difficulty_walking	14006	14006	14006
	afraid_to_get_hurt_by_movement	14006	14006	14006
	patient_acceptable_symptom_state	14006	14006	14006
	motivation_readiness	14006	14006	0
	overall_health_improved	0	0	4329
	physical_function_improved	0	0	4329
	considers_treatment_failed	0	0	8857
	wants_operation	14006	14006	14006
	invasive_operation_scheduled	2337	2337	2176
	arthroscopy_performed_on_specific_joint	14006	14006	0
	invasive_operation_type_scheduled	299	299	0
	invasive_operation_cancelled	0	0	1571
Medication	invasive_medicines_selections			
	invasive_medicines_changed			
EQ-5D	eq5d.mobility	14006	14006	14006
	eq5d.self_care	14006	14006	14006

	eq5d.pain_discomfort	14006	14006
	eq5d.usual_activities	14006	14006
	eq5d.anxiety_depression	14006	14006
HOOS-PS	hoos.running_difficulty		
	hoos.sitting_difficulty		
	hoos.descending_stairs_difficulty		
	hoos.getting_out_of_bath_difficulty		
	hoos.pivoting_loaded_leg_difficulty		
KOOS-PS	koos.squatting_difficulty		
	koos.sitting_up_difficulty		
	koos.bending_over_difficulty		
	koos.twisting_knee_difficulty		
	koos.laying_on_knee_difficulty		
	koos.putting_on_socks_difficulty		
	koos.rising_out_of_bed_difficulty		
Work productivity	wpai.employed		
	wpai.hours_actually_worked		
	wpai.oa_productivity_effect		
	wpai.oa_regular_activities_effect		
	wpai.missed_working_hours_due_to_oa		
	wpai.missed_working_hours_due_to_other_reasons		
JA	ja_like		
	recommend_others		
	therapist_appreciation		
Other	free_text_medical_information		
HIP new	hip_satisfaction_now	0	3956
	hip_satisfaction_quality	0	3956
	hip_satisfaction_performance	0	3956
	hip_satisfaction_symptoms_now	0	3956
	hip_satisfaction_sports_performance	0	3956
HOOS-12 new	hoos.standing	3541	3956
	hoos.in_out_car	3541	3956
	hoos.hip_aware	3541	3956
	hoos.going_stairs	3541	3956
	hoos.sitting_lying	3541	3956
	hoos.rising_sitting	3541	3956
	hoos.hip_confidence	3541	3956
	hoos.hip_difficulty	3541	3956
	hoos.hip_pain_duration	3541	3956
	hoos.walk_flat_surface	3541	3956
	hoos.modified_lifestyle	3541	3956

	hoos.walk_uneven_surface	3541	3956
KNEE new	knee_satisfaction_now	0	5721
	knee_satisfaction_quality	0	5721
	knee_satisfaction_performance	0	5721
	knee_satisfaction_symptoms_now	0	5721
	knee_satisfaction_sports_performance	0	5721
KOOS-12 new	koos.standing	5026	5721
	koos.in_out_car	5026	5721
	koos.knee_aware	5026	5721
	koos.going_stairs	5026	5721
	koos.sitting_lying	5026	5721
	koos.rising_sitting	5026	5721
	koos.knee_confidence	5026	5721
	koos.knee_difficulty	5026	5721
	koos.knee_pain_duration	5026	5721
	koos.walk_flat_surface	5026	5721
	koos.modified_lifestyle	5026	5721
	koos.twisting_injured_knee	5026	5721

**Fig. 1 Flowchart**
